SC=subcutaneous; T=testosterone; TFA=Trifluoroacetate For participants in Group 2, the following actions will be taken at the Day 28 visit based on the results of the locally analysed T level determined from the Day 21 visit:

[T] (ng/mL)	Action Taken	Dose Administered
≤2	Continue with Stage 2 of Group 2	No dose on Day 28. Maintenance dose of 180 mg SC teverelix TFA every 42 days
>2	Withdraw from study; safety follow-up visit on Day 28	None

SC=subcutaneous; T=testosterone; TFA=Trifluoroacetate

Day 35 Visit

On Day 35, local testing of T levels will be performed to guide decision making at the Day 42 visit. PK, total T, LH, FSH and PSA (total and high-sensitivity [hs]) samples will also be collected for central laboratory analysis.

Stage 2 Visits in Groups 1 and 2

Day 28 Visit

Stage 2 will start at the Day 28 visit. However, participants will receive their first maintenance dose at the Day 42 visit and participants will visit the clinic at Day 35 to provide a blood sample for local laboratory testing of T levels.

Blood samples for PK and PD analyses (T, LH, FSH, PSA), and fasted (≥8 hours) safety laboratory testing will be collected. Samples will also be collected for urine analysis. AE assessment, physical examination, triplicate 12-lead ECG and assessment of vital signs (including sitting blood pressure and heart rate) will be performed.

If, in the opinion of the investigator, no safety concerns exist, participants will be discharged from the centre.

Visits at Day 42, Day 84, Day 126, and Day 168

On Day 42 the first maintenance dose will be administered.

Before administration of the maintenance dose, blood samples for PK and PD analyses as well as fasted (≥8 hours) safety laboratory testing will be collected. Samples will also be collected for urine analysis. Pre-dose AE assessment (including ISR), physical examination, triplicate 12-lead ECG and assessment of vital signs (including sitting blood pressure and heart rate) will be performed.

Participants will attend the clinic 1 week before each maintenance dose is given (i.e. at Days 35, 77, 119 and 161) to provide a blood sample for local laboratory assessment of T levels. At the Day 35 visit (only) PK, total T, LH, FSH and PSA (total and hs) samples will also be collected for central laboratory analysis. Based on the results of the local analysis of T level from 7 days prior to the scheduled visit, participants will receive:

[T] (ng/mL)	Action Taken	Dose Administered

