AEs: All AEs will be coded using Medical Dictionary for Regulatory Activities (MedDRA) terminology and summarised by PT and SOC. Frequencies of AEs will be presented by absolute and relative frequencies of (a) the number of AEs and (b) the number of participants experiencing an event for each SOC and PT.

AEs will be summarised separately for serious AEs, treatment-emergent AEs (defined as any new or worsening pre-existing AE with a date equal to or later than the date of IMP administration) and possibly treatment-related AEs.

PK/PD: Concentrations over time will be described by area under the concentration-time curve from time zero to last available measurement (AUC_{0-t}), maximum concentration (C_{max}), time to reach maximum concentration (T_{max}), terminal half-life ($t_{1/2}$), first-order elimination rate and graphical representation of the concentrations over time. The geometric mean will be calculated additionally for AUCs and C_{max} .

Depending on the progression of the concentrations, multiple peaks of concentrations can occur. Additional AUC, T_{max} and C_{max} will be specified accordingly (total and separated by each phase of concentration increase) for the parameters.

Missing data will not be substituted in general, but in the case of a laboratory reporting concentrations as unquantifiably low, they will be set to 0.

All study data will be reported in participant data listings.

Detailed statistical methodology, definitions and data handling will be described in a separate statistical analysis plan (SAP) prior to analysis.

Responsibilities

Sponsor's Responsible Representative:	[name]
The second secon	VP Women's Health & Clinical Operations
	Antev Limited
	[name]
	London
	[name]
	UK
	Email: [contact]
Sponsor's Medical Expert:	[name]
The second secon	Chief Scientific Officer
	Antev Limited
	[name]
	London
	[name]
	UK
	Email: [contact]
Medical Lead Insuvia UAB:	[name]
	Clinical Research Physician
	[name]
	[name]
	[contact]
Biometrician Quanticate International	[name]
Ltd:	Senior Statistician I
	[name]
	[name]
	Email: [contact]
Pharmacokinetic Laboratory:	[name]
	Senior Scientist Small Molecule Bioanalysis
	Drug Development Solutions
	LGC
	[name]
	Fordham Cambridgeshire
	[name]
	UK
	[contact] [name]
	Email: [contact]

ANT-1111-02, Teverelix TFA in Prostate Cancer FINAL Version 5.0, 31 May 2022 Page 16 of 84

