DAY 21 [T]	DAY 28: No teverelix TFA dose
DAY 35 [T]	DAY 42: Maintenance dose 120 or 180 mg SC
DAY 77 [T]	DAY 84: Maintenance dose 120 or 180 mg SC
DAY 119 [T]	DAY 126: Maintenance dose 120 or 180 mg SC
DAY 161 [T]	DAY 168: Maintenance dose 120 or 180 mg SC
*DAY 203 [T]	No dose
*DAY 210 [T]	No dose
*DAY 217 [T]	No dose
*DAY 224 [T]	No dose
*DAY 231 [T]	No dose
*DAY 238 [T]	No dose
*DAY 245 [T]	No dose
*DAY 252 [T]	No dose

SC=subcutaneous; T=testosterone

^{*}Group 2 subjects with Stage 3 only

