6.4 Pharmacokinetics

6.4.1 Pharmacokinetic Variables

Pharmacokinetic parameters will be generated using Phoenix WinNonlin Version 6.4 or higher for evaluation.

The concentrations of all participants who successfully complete the study will be analysed and samples of withdrawn or dropout participants will not be analysed. This analysis may include the parameters shown in Table 12. Full details will be presented in the statistical analysis plan (SAP).

Table 12: Pharmacokinetic Parameters

PK	Description	Unit
Parameter		
AUC _{0-t}	Area under the concentration-time-curve from time zero up to	ng•h/
	the last measurable concentration at timepoint t	mL
AUC_{0-t1}	Area under the concentration-time-curve from time zero up to	ng•h/
	concentration at timepoint t1 after which the concentrations start	mL
	to rise again towards a second peak, t1 will be determined after	
	review of the concentration-time profiles (immediate release	
	component of total observed AUC)	

PK	Description	Unit
Parameter	-	
AUC _{t1-t}	Area under the concentration-time-curve from timepoint t1 up to	ng•h/
	timepoint t (slow release component of total observed AUC)	mL
$\mathrm{AUC}_{0\text{-}\infty}$	Area under the concentration-time-curve from time zero up to	ng•h/
	infinity (∞)	mL
C_{max}	Maximum plasma concentration	ng/mL
$C_{max,0-t1}$	Maximum plasma concentration after administration from zero up to timepoint t1	ng/mL
C _{max,t1-t}	Maximum plasma concentration after administration from timepoint t1 up to timepoint t	ng/mL
T_{max}	Time to reach C_{max} after dosing	h
$T_{max,0-t1}$	Time to reach $C_{max,0-t1}$ after dosing	h
T _{max,t1-t}	Time to reach $C_{max,t1-t}$ after dosing	h
$\lambda \mathbf{z}$	Apparent terminal rate constant	1/h
t ½	Apparent terminal plasma half-life	h

h=hours; PK=pharmacokinetic

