**Table 16 Pharmacokinetic Parameters**

PK parameter	Description	Unit
AUC0-t	Area under the concentration time-curve from time zero up to the last quantifiable concentration at time point t ( $C_t$ ), calculated using the linear up/log down trapezoidal rule.	ng*h/mL
AUC0-t1	Area under the concentration time-curve from time zero up to the concentration at time point t1 after which the concentrations start to rise again towards a second peak, calculated using the linear up/log down trapezoidal rule. t1 will be determined after review of the concentration-time profiles (immediate release component of total observed AUC).	ng*h/mL
AUCt1-t	Area under the concentration time-curve from time point t1 up to the concentration at time point t (slow release component of total observed AUC), calculated using the linear up/log down trapezoidal rule.	ng*h/mL
AUC0-∞	Area under the concentration time-curve from time zero up to infinity ( $∞$ ), calculated using the linear up/log down trapezoidal rule.	ng*h/mL
Cmax	Maximum plasma concentration	ng/mL
Cmax,0-t1	Maximum plasma concentration after administration from zero up to time point t1	ng/mL
Cmax,t1-t	Maximum plasma concentration after administration from time point t1 up to time point t	ng/mL
tmax	Time to reach $C_{max}$ after dosing	h
tmax,0-t1	Time to reach $C_{max,0-t1}$ after dosing	h
tmax,t1-t	Time to reach $C_{max,t1-t}$ after dosing	h
tlast	Time of the last quantifiable concentration	h
λz	Apparent terminal elimination rate constant	1/h
t½	Apparent terminal plasma half-life, calculated as: $\ln 2 / \lambda_z$	h

h= hours; PK= Pharmacokinetic

Document:

C:\ProgramData\activePDF\Temp\DocConverter\API\Input\\$651f4dc0b253\$FE3041C5883446E892B20AB6D3F0E1BD.docx

Author: [name]

Version and Date: Version 1.0, 21 Apr 2023

Page 49 of 66

Actual sampling times (relative to the IM injection of teverelix TFA at time zero) will be used for the calculation of all PK parameters, and all calculations will be made using non-rounded raw data. Where the actual sampling time is not recorded, the nominal sampling time will be used. Concentrations below the lower limit of quantification (LLOQ) will be taken as zero for calculation of concentration summary statistics and PK parameters.

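### As defined, AUC0-t, AUCt1-t and AUC0-inf run from Day 0 across four maintenance doses that are sampled only before dosing, so they measure neither loading-dose nor cumulative exposure

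*Protocol*

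**What the plan says.** **End point of the area.** The protocol synopsis (Statistical Methods, PK/PD) says: "Concentrations over time will be described by area under the concentration-time curve from time zero to last available measurement". SAP Table 16 defines AUC0-t as "Area under the concentration time-curve from time zero up to the last quantifiable concentration at time point t", by the linear-up/log-down trapezoid. AUCt1-t has the same open end: "Area under the concentration time-curve from time point t1 up to the concentration at time point t (slow release component of total observed AUC". Protocol Table 12 uses the same definitions, and AUC0-inf extrapolates from the same last concentration.

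**Time origin.** Below Table 16 the SAP adds: "Actual sampling times (relative to the IM injection of teverelix TFA at time zero) will be used for the calculation of all PK parameters". The intramuscular injection is given on Day 0 only.

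**Doses.** Protocol Table 4 lists four maintenance injections, from "DAY 42: Maintenance dose 120 or 180 mg SC" to "DAY 168: Maintenance dose 120 or 180 mg SC", with the others on Days 84 and 126.

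**Samples.** On those visits the draw comes first: "Before administration of the maintenance dose, blood samples for PK and PD analyses". Days 77, 119 and 161 have local testosterone only. After Day 168, participants without Stage 3 have PK at one follow-up visit 28 days later (Protocol 7.2.4). Group 2 Stage 3 participants have PK on Day 203, weekly to Day 252 at most, and at the final assessment (Protocol 7.2.5; Table 13, note d).

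**Safeguards.** SAP 4.3.8.1 requires at least three points in the terminal phase, withholds half-life if Rsq is below 0.8, and flags AUC0-inf if more than 20% is extrapolated. It also flags a terminal-rate window shorter than two half-lives. Further PK detail is left to a separate PK SAP.

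**The concern.** An area from zero to the last concentration is a single-dose measure. Here the same rule is applied to a profile with five dosing days. After Day 42 the trapezoid joins one pre-dose trough to the next and misses each rise in between, so later injections add to the area but far too little. AUCt1-t is labelled the slow-release component, yet it would include four later injections.

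The end point also depends on follow-up: about Day 196 without Stage 3 and up to Day 259 with it. Within Stage 3, sampling ends 7 days after local testosterone reaches 1 ng/mL, so the length of the area depends on the pharmacodynamic response.

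Describing the PK profile is a stated secondary objective and PK parameters are a listed secondary endpoint. Read as total or loading-dose exposure, the tabulated AUCs would mislead anyone who used them to compare regimens or to build an exposure-response argument.

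**Working it through.** The plan states no numerical PK result, so there is nothing to reproduce. The sample counts below come from the documents. The bias sizes rest on assumed kinetics.

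**1. Samples per dosing interval** (synopsis sampling list, Protocol Table 13, Sections 7.2.2 to 7.2.5)

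| Interval | Samples strictly inside |
|---|---|
| Day 0 to 42 | 10 (1 to 24 h) + 2 (48, 72 h) + 6 (Days 4, 7, 10, 12, 14, 21) + 2 (Days 28, 35) = 20 |
| Day 42 to 84 | 0 |
| Day 84 to 126 | 0 |
| Day 126 to 168 | 0 |
| After Day 168, no Stage 3 | 1 (168 + 28 = Day 196) |
| After Day 168, Stage 3 | 2 (Days 203 and 210, if testosterone reaches 1 ng/mL at Day 203) to 9 (Days 203 to 252 weekly = 8, plus Day 259) |

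One sample after the last dose is below the SAP's own minimum of three terminal points.

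**2. One maintenance interval, simplest case** (assumption: mono-exponential decline, steady state)

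With x = 42 × ln 2 / half-life, the trough-to-trough area divided by the true area is x / (e^x − 1).

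- Half-life 14 days: 2.079 / (8 − 1) = 0.297
- Half-life 21 days: 1.386 / (4 − 1) = 0.462
- Half-life 28 days: 1.040 / (2.828 − 1) = 0.569

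**3. Whole profile to Day 196** (same assumption; loading dose 2 units, each maintenance dose 1 unit)

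For a 14-day half-life the sampled concentrations on Days 42, 84, 126, 168 and 196 are 0.250, 0.156, 0.145, 0.143 and 0.286. The trapezoid gives 35.3 (Days 0 to 42) + 8.4 + 6.3 + 6.0 + 6.0 = 62.0. The true area is the sum over doses of dose × (1 − 2^(−d/14)) × 14 / ln 2, where d is days from dose to Day 196: 40.4 + 20.2 + 20.1 + 19.6 + 15.1 = 115.4. The ratio is 62.0 / 115.4 = 0.54. The loading-dose AUC0-inf is 40.4, so the literal area is also 62.0 / 40.4 = 1.53 times that quantity. It matches neither target. For a 28-day half-life the same steps give 146.4 / 211.0 = 0.69.

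**4. Depot-type model** (assumptions: fast fraction 0.1 or 0.3; slow-depot half-life 7, 14, 21 or 30 days; elimination half-life 0.5 or 1.5 days)

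| Quantity | Range over the 16 combinations |
|---|---|
| Literal AUC0-t / true exposure, to Day 196 | 0.38 to 0.68 |
| Literal AUC0-t / true exposure, to Day 259 | 0.37 to 0.71 |
| Literal AUC0-t / loading-dose AUC0-inf | 1.12 to 2.06 |
| Half-life from whole profile, no Stage 3 | 25 to 147 days (assumed 7 to 30), Rsq 0.52 to 0.65 |
| Half-life from full Stage 3 samples | 7.0, 14.0, 21.0, 30.0 days (as assumed) |
| Trapezoid / true area, Day 0 to 42 only | 1.00 to 1.01 |

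The last row shows that the existing schedule measures loading-dose exposure well once the end point is set.

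**The case against.** The strongest defence is deferral. The SAP calls its PK content general information and sends the analysis to a PK SAP that is not among the documents, and Protocol 8.1.4 reserves parameter formulas and the terminal rate for later. The PK SAP may well set the end point. But SAP 4.3.8.1 already says which parameters will be analysed and defines each one, so the PK SAP would have to depart from those definitions.

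The synopsis also allows extra AUC, Cmax and Tmax for each phase of rising concentration, and SAP 3.6 lets a profile be excluded by period. Neither helps here: the rises after maintenance doses are never sampled, and only one split point, t1, is defined.

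Several stronger readings are tempting but the documents do not support them:

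- *A reader might infer that no elimination half-life can be obtained.* Stage 3 participants with at least three samples after Day 168 have a dose-free terminal phase. Without Stage 3, the three-point and Rsq rules would largely withhold a spurious value, so the harm is mainly a lost estimate. Those rules do not protect AUC0-t or AUCt1-t.
- *A reader might infer that early withdrawal gives AUCs ending at Day 28.* Protocol 6.4.1 leaves withdrawn participants' samples unanalysed, and the SAP's PK set lies within the per-protocol set, which requires study completion.
- *A reader might infer that every PK parameter is affected.* AUC0-t1, Cmax,0-t1 and Tmax,0-t1 rest on the rich loading-dose sampling and stand if t1 falls before Day 42.
- *A reader might infer that dose selection or a group comparison is biased.* The sample-size section ties support for dose selection to the Day 28 testosterone response, and the two groups are analysed separately.

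**Conclusion.** The point holds for AUC0-t, AUCt1-t and AUC0-inf. As defined, they cross four maintenance doses, with no sample between dose and next trough in three intervals and one sample after the last dose without Stage 3. They are neither loading-dose nor cumulative exposure, AUCt1-t is not the slow-release component of the loading dose, and t varies with follow-up. Half-life from the end of the whole profile is unsupported in participants without Stage 3; it can be estimated in Stage 3 participants with three or more samples after Day 168.

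The sample counts need no assumption. The size does: literal AUC0-t is roughly 40% to 70% of true exposure under the kinetics tried, none of which comes from the documents. Treat that range as illustrative. The primary testosterone endpoint is untouched. This should be corrected before the PK analysis is run.

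**What to change.** Amend SAP Table 16 and write the same rules into the PK SAP. Either align the protocol wording or list the change in SAP 7.1.

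- End AUC0-t, AUCt1-t, and the overall and t1-to-t Cmax and Tmax at the Day 42 pre-dose sample. Leave the 0-to-t1 parameters as they are.
- Report Days 84, 126 and 168 as trough concentrations.
- Estimate the terminal rate and half-life only within one dose-free interval: Day 0 to 42, or Stage 3 with time reset to the Day 168 injection.
- Report AUC0-inf only by extrapolation from the Day 0 to 42 profile, under the existing 20% flag.

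No new samples are needed. The cost is wording, plus a formal amendment if the protocol text itself is changed. AUC would then describe the loading dose only, and maintenance exposure would be seen only as troughs. If release is slow, the existing flags will be triggered. In the depot model, Days 0 to 42 capture 0.64 to 0.73 of AUC0-inf at a 30-day depot half-life, so 27% to 36% is extrapolated. A 42-day window holds two half-lives only if the half-life is at most 42 / 2 = 21 days. Those flags would correctly show what the design cannot estimate well.

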ALAT Alanine aminotransferase APC Advanced prostate cancer ASAT Aspartate aminotransferase

ATC Anatomical Therapeutic Chemical Classification

 $AUC_{0-\infty}$ Area under the concentration-time-curve from time zero up to

infinity (∞)

 AUC_{0-t} Area under the concentration-time-curve from time zero up to

the last measurable concentration at timepoint t

 AUC_{0-t1} Area under the concentration-time-curve from time zero up to

concentration at timepoint t1 after which the concentrations

start to rise again towards a second peak

AUC_{t1-t} Area under the concentration-time-curve from timepoint t1 up

to timepoint t (slow release component of total observed

AUC)

BMI Body mass index BP Blood pressure

BPH Benign prostatic hyperplasia

CI Confidence interval

C_{max} Maximum plasma concentration

C_{max,0-t1} Maximum plasma concentration after administration from

zero up to timepoint t1

C_{max,t1-t} Maximum plasma concentration after administration from

timepoint t1 up to timepoint t

CRA Clinical research associate
CRO Clinical Research Organisation

CTCAE Common Terminology Criteria for Adverse Events

ECG Electrocardiogram(s)
eCRF Electronic case report form

EudraCT European Union Drug Regulating Authorities Clinical Trials

FDA Food and Drug Administration FSH Follicle stimulating hormone GCP Good Clinical Practice

GMP Good Manufacturing Practice
GnRH Gonadotropin-releasing hormone

HbA1c glycated haemoglobin

HIV Human immunodeficiency virus

hsTn High sensitivity troponin ICF Informed consent form

ICH International Conference on Harmonisation

IEC Independent Ethics Committee

IM Intramuscular

IMP Investigational medicinal product

ANT-1111-02, Teverelix TFA in Prostate Cancer

FINAL Version 5.0, 31 May 2022

Page 21 of 84

I-PSS International Prostate Symptom Score

IRB Institutional Review Board
ISI Injection site inspection
ISR Injection site reaction(s)

ITT Intention-to-treat IV Intravenous

L Litre

LH Luteinising hormone

MedDRA Medical Dictionary for Regulatory Activities

mg Milligram mL Millilitre

mmHg Millimetre of mercury

msec Millisecond ng Nanogram nmol Nanomole

NT proBNP B-type natriuretic peptide

PD Pharmacodynamic
PK Pharmacokinetic
PP Per protocol

PSA Prostate-specific antigen

PT Preferred term
QoL Quality of Life

OTcF Fridericia corrected OT interval

SAE Serious adverse event SAP Statistical analysis plan

SCSubcutaneousSDStandard deviationSOCSystem organ class

SOP Standard operating procedure

1.1 Background

Prostate cancer is the most commonly diagnosed cancer in men, and the second leading cause of cancer-related deaths [1]. Most prostate cancer-related deaths are due to advanced disease, which results from any combination of lymphatic, haematogenous, or contiguous local spread.

1.1.1 Epidemiology of Advanced Prostate Cancer

Approximately 11.6% of men will develop prostate cancer in their lifetime, with the likelihood increasing with age. Prostate cancer is most often diagnosed in men aged between 55 and 74 years, with a median age at diagnosis of 66 years [2]. Since the advent of prostate-specific antigen (PSA) screening, prostate cancer is being detected and treated earlier.

Overall, incidence rates of prostate cancer began declining in 2000. Acceleration in the decline began in 2008, when health organisations started to argue against routine PSA screening. From 2009 to 2013, the incidence rate decreased by approximately 8% per year [1].

A review of almost 800,000 cases of prostate cancer diagnosed from 2004 to 2013 found that although the incidence of low-risk prostate cancer decreased between 2007 to 2013 to 37% less than that of 2004, the annual incidence of metastatic prostate cancer during those years increased to 72% more than that of 2004. The increase in metastatic prostate cancer was greatest (92%) in men aged 55 to 69 years [3].

At diagnosis, 79% of prostate cancer cases are localised; in 12%, the cancer has spread to regional lymph nodes, and in 5% there are distant metastasis. The 5-year relative survival rate for localised and regional prostate cancer is 100%, compared with 29.8% for metastatic cases [2].

Since the early 1990s, prostate cancer death rates have been decreasing in men of all races and ethnicities. However, they remain more than twice as high in black men as in any other group [1]. Prostate cancer tends to not only be more aggressive and progressive in black men, leading to advanced disease, but to also be of a higher grade at diagnosis [4, 5]. Death rates are also higher in men who have advanced-stage cancer, and in men who are 75 to 84 years of age [2]. The mortality rate associated with prostate cancer continues to increase in Europe and in countries such as Australia, Japan, and Russia.

1.1.2 Presentation of Advanced Prostate Cancer

Advanced prostate cancer results from any combination of lymphatic, blood, or contiguous local spread. Manifestations of metastatic and advanced disease may include the following:

- Anaemia
- Bone marrow suppression

NTEV

Page 27 of 84

- Weight loss
- Pathologic fractures
- Spinal cord compression
- Pain
- Haematuria
- Ureteral and/or bladder outlet obstruction
- Urinary retention
- Chronic renal failure
- Urinary incontinence
- Symptoms related to bony or soft-tissue metastases

Treatment-related symptoms (sometimes associated with radiation therapy), such as rectal bleeding, gross haematuria, and urethrorectal fistula, need to be differentiated from the disease-specific symptoms.

Physical examination findings of adenopathy, lower-extremity oedema, and bony tenderness may indicate metastatic disease. In addition, obliteration of the lateral sulcus or seminal vesical involvement found during rectal examination often indicates locally advanced disease. Neurologic examination, including determination of external anal sphincter tone, should be performed to help detect possible spinal cord compression.

1.1.3 **Treatment Overview**

Several treatment options exist for different stages of prostate cancer, including observation, prostatectomy, radiation therapy, chemotherapy, and hormone therapy. Hormone therapy has evolved from the use of oestrogens to gonadotropin-releasing hormone (GnRH) agonists and recently, investigational GnRH antagonists [6].

Androgen deprivation therapy (ADT) is the backbone of treatment for participants with advanced prostate cancer, and it is indicated for use in multiple clinical settings of prostate cancer. Chemical castration consists of GnRH agonists and antagonists administered intramuscularly (IM), subcutaneously (SC), or orally. One of the main concerns when using GnRH agonists is a surge in testosterone (T) caused by the medication's initial effect on the pituitary gland. This T surge could lead to a tumour flare, which is characterised by a rapid expansion of the prostate cancer, leading to pain and potential debilitation, particularly in participants with spinal metastases. This concern of tumour flare led to the development of the GnRH antagonists, which do not cause a T surge, since there is no initial stimulation of the pituitary gland by the medication. The GnRH antagonist degarelix is currently approved by the US Food and Drug Administration (FDA) for the treatment of participants with advanced prostate cancer [7].

GnRH antagonists are analogues of GnRH, and act as a competitive inhibitor of GnRH [8]. GnRH mediates stimulation of gonadotropin (i.e., follicle stimulating hormone [FSH] and luteinising hormone [LH]) secretion [9]). Unlike GnRH agonists, the GnRH antagonists do not cause an initial surge of gonadotropins. They rapidly decrease the secretion of LH and FSH from the pituitary gland, thereby leading to an immediate decrease in T secretion from the Leydig cells of the testicles [10].

